3.2 Analysis Populations

3.2.1 Enrolled Population

The enrolled population is defined as all subjects randomized into the trial.

3.2.2 Randomly Assigned to Study Intervention Population

The randomly assigned to study intervention population is defined as all subjects who received a dose or partial dose of study drug.

3.2.3 Intent-to-Treat (ITT) Population

The ITT Population will be the primary population for analysis of efficacy data.

The ITT Population is defined as all randomized subjects who received study drug. Their data will be analyzed according to the randomized treatment, regardless of treatment actually received. Subjects who receive treatment but do not get the full 48 hours of treatment will be included in the ITT analysis. The full 48-hour treatment time is considered +/- 4 hours from the intended infusion stop time. Any randomized subjects who did not receive treatment will be excluded from the ITT population.

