Statistical Assumptions	Analyses will be examined on the intent-to-treat (ITT) sample, defined as all randomized participants, regardless of treatment actually received. The per protocol sample will also be examined separately. Patients who receive treatment but do not get full 48 hours of treatment due to fluid overload or early discharge will be included in the ITT analysis. Patients who complete the full 48 hours will be included in both per protocol and ITT analysis.

	
All analyses will be accomplished using SAS Software 9.4 (SAS Inc. Cary, NC). Primary: The frequency of SAEs, SAEs resulting in death, AEs, and discontinuations due to AEs will be summarized as counts and percentages between the three arms. Comparisons will be conducted using Fisher's Exact tests.
 
Secondary: Comparisons between conditions for mRS will be evaluated using generalized mixed modeling assuming a binomial distribution (0-6) with sandwich estimation nested by site and patient, when applicable. Pairwise comparisons of mRS will be conducted at Day 90 using a Dunnett correction. In addition, simple and interaction effects between pre-stroke, discharge, 30-day and 90-day mRS by condition will be examined. Both NIHSS and BI at Day 90 will be examined in a similar fashion assuming a binomial distribution (0-42 & 0-100) with sandwich estimation. Pairwise comparisons between conditions will be conducted at Day 90 using a Dunnett correction. In addition, simple and interaction effects between pre-treatment, discharge, 30-day and 90-day NIHSS and BI by condition will be examined. Mortality will be examined using Kaplan-Meier estimation with pairwise comparisons with a Dunnett correction. DWI volume post treatment and at 48 hours, and 90-day T2 will be modeled between conditions using generalized linear modeling assuming a normal or lognormal distribution (where appropriate), where simple and interaction effects will be examined. Because superiority over placebo and lower dose is hypothesized, testing will reflect this superiority framework. Because the main aim of this trial is to examine safety, efficacy analysis results are intended to yield estimates to inform powering for a future efficacy trial. Alpha is established at the 0.05 level and all interval estimates will be calculated for 95% confidence.

Data Safety Monitoring Board	A Data Safety Monitoring Board (DSMB) will monitor patient safety and scientific integrity during the trial.

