5.5 Study Enrollment Process

In this AIS trial, patients should be randomized into the trial and receive study drug as soon as possible (within 30 minutes of randomization and before completion of EVT procedure as defined by completion of arterial access closure), following review of trial eligibility and the local informed consent process. Participants will be identified using usual standard of care screening methods at the acute stroke hospital. All participants will undergo an acute clinical assessment, blood laboratory assessment, baseline electrocardiogram, baseline chest radiograph, and baseline brain imaging. Due to the short time-period from arrival at the hospital to the EVT, the results of the baseline blood work and the results from the initial ECG and CXR are not required prior to randomization or start of infusion.

If the participant remains eligible after completion of routine stroke screening, the patient will be consented (as required) and enrolled into the trial. A participant is considered randomized the moment the randomization process is completed on-line. Participants who are randomized but do not receive study drug will still be followed through the 90-day study period.

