6.3 Measures to Minimize Imbalance: Block Urn Randomization and Blinding

All patients will be centrally assigned to a randomized study intervention (i.e. RNS60 0.5 mL/kg/h, RNS60 1mL/kg/h, or placebo 1 mL/kg/h) using block urn randomization tables (8 urns). The randomization table will be set for up to 100 people per urn to ensure no urn can be filled prior to enrollment completion. Each site will have their own randomization table.

Treatment allocation will be assigned using 1:1:1 randomization (RNS60 0.5 mL/kg/h, RNS60 1 mL/kg/h, or placebo 1 mL/kg/h). Randomized allocation will be fully concealed by having allocations based upon random assignment and blinded by the use of visually identical appearing RNS60 and placebo infusion bags. All infusion bags will have a unique number.

The purpose of using block urn randomization is to minimize the possibility of imbalance of treatment assignment by age, NIHSS score, and ASPECTS due to the small sample size.

All participants, investigators, their clinical staff, local and central laboratories, the clinical coordinating center, the data management group, and the sponsor staff and delegates will be blinded to the randomization codes.

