7.2 Participant Discontinuation/Withdrawal from the Trial

Participation in this clinical trial may be discontinued for any of the following reasons:

- Administrative reasons (uncooperative, noncompliant, etc.)
- Participant's decision not to participate any further
- If it is in the participant's best interest, per the qualified/principal or sub-investigator

If the participant or legally authorized representative (LAR) withdraws consent, participant data will be included in the analysis up to the date of the consent withdrawal and this withdrawal of consent will be documented in the CRF.

If the LAR has originally provided consent and the participant subsequently declines consent, this will be deemed to be a withdrawal of consent. The investigator and sponsor would continue to have access to data that have already been collected.

A participant may not withdraw use of his or her data that have already been collected. This is in alignment with the FDA guidance document "Data Retention When Participants Withdraw from FDA-Regulated Clinical Trials", which is based on the importance of avoiding selection biases that could compromise the analysis of the overall trial.

Otherwise, all randomized participants will continue to be followed according to protocol requirements and follow-up data will be included in the analysis. Criteria for removal of participants will be recorded and reported.

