9.2 Analysis Sets

For purposes of analysis, the following populations are defined:

Population	Description
Intent to Treat (ITT)	All participants randomized into the trial with grouping by randomized treatment, regardless of whether any treatment was actually received. Participant grouped according to the randomized (intended) treatment. (Participant who receive treatment but do not get the full 48 hours of treatment due to fluid overload, early discharge, or death will be included in the ITT analysis.)
Per Protocol	All participants randomized and treated, with no major protocol deviations including: did not meet inclusion/exclusion criteria, did not receive planned dose volume, incorrect study drug, consent not obtained (Participant who completes the full 48 hours will be included in both per protocol and ITT analysis.)
Full Analysis Set / Safety	All participants randomly assigned to study intervention and who receive any volume of study drug. Participants will be analyzed according to the intervention they actually received.

The primary efficacy analysis will be conducted in the ITT population. The primary analysis will be repeated on the per protocol population. An ITT analysis will also be conducted for the secondary endpoints, with participant grouped according to the randomized (intended) treatment.

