1 INTRODUCTION

The purpose of this statistical analysis plan (SAP) is to provide a description of the statistical methods to be implemented for the analysis of data from the study with protocol number 06.5.1.H1 dated 09 May 2022 (version 2.4). The SAP will be finalized prior to database lock. Any future addendum to the SAP (if applicable) will be referenced in the Clinical Study Report (CSR).

The SAP will be considered as the governing document and in case of any differences between this SAP and the study protocol, the SAP will supersede the protocol.

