The attributes of the main estimand (target of estimation), used for the primary analysis of the highest ranked efficacy endpoint (modified Rankin Scale (mRS) score) are defined below. Although the primary objective of this study is related to safety, analysis of the efficacy endpoints (secondary objectives of the study) will be based on a pre-defined hierarchy and therefore, an estimand is defined.

- The **population** is defined as the intent-to-treat study population (see Section 3.2.3).
- The corresponding **variable** to be obtained for each subject required to address the scientific question is disability based on the mRS score at Day 90. The mRS will be evaluated as a binary outcome (0-2, 3-6).
- The **population level summary** considered in this study is the odds ratio between RNS60 1.0 mL/kg/h and placebo 1.0 mL/kg/h.
- The **treatments** to be compared are RNS60 1.0 mL/kg/h and placebo 1.0 mL/kg/h. The treatments will be compared according to the randomized groups, regardless of the treatment that was actually received. In accordance with the treatment policy principle, all available data will be used in the analysis, regardless of e.g., premature discontinuation of study medication or administration of any concomitant treatment.
- The **intercurrent events** (ICEs) considered as potentially impacting results and/or interpretation are:
 - Premature discontinuation of study treatment
 - Death
 - Coronavirus Disease 2019 (COVID-19) pandemic related events (assessments that were missed due to COVID-19).

For the data that are missing due to premature discontinuation of study treatment, an assumption of Missing At Random (MAR) will be made. Sensitivity analyses will be conducted using an assumption of Missing Not At Random (MNAR). No specific imputation will be done for these missing data, because the likelihood-based analysis approach can manage subjects with incomplete data under the assumption of MAR.

For the data that are missing due to COVID-19, an assumption of MAR will be made for all analyses, both primary and sensitivity analyses.

For the mRS, NIHSS and BI endpoints death is included as part of the scoring, so no imputation of these endpoints is required for subjects who die. Similarly, for the worsening of stroke endpoint, death represents a worsening. For the infarct progression end point, death will be represented by a missing value.

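### The SAP gives the name ITT to a randomised-and-dosed set, so no planned efficacy analysis covers all randomised patients as the protocol requires

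*SAP*

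**What the plan says.** **Protocol.** Section 9.2 defines the ITT set as "All participants randomized into the trial with grouping by randomized treatment, regardless of whether any treatment was actually received" and places the primary efficacy analysis in it. The Synopsis agrees: ITT is "defined as all randomized participants, regardless of treatment actually received". Section 9.2 has a different name, Full Analysis Set / Safety, for patients who were randomised and received any volume of drug. Section 5.5 plans outcome data for the undosed: "Participants who are randomized but do not receive study drug will still be followed through the 90-day study period". Section 7.2 adds that, consent withdrawal aside, "all randomized participants will continue to be followed according to protocol requirements and follow-up data will be included in the analysis".

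**SAP.** Section 3.2.3 limits ITT to randomised subjects who received study drug and then states: "Any randomized subjects who did not receive treatment will be excluded from the ITT population". Section 3.2.4 (Per-Protocol) also requires study drug. Section 3.4 runs efficacy in these two sets. The Enrolled Population (3.2.1) is the only all-randomised set, and no efficacy analysis is assigned to it. The estimand in 2.1.3 takes its population from 3.2.3. Section 6.4 reports the new definition as a clarification, without a reason. Section 1 says that "in case of any differences between this SAP and the study protocol, the SAP will supersede the protocol".

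**The concern.** The protocol's efficacy population has been replaced, under the same name, by one defined by an event after randomisation: whether the infusion was started. The protocol collects Day 90 data on undosed patients and says they will be analysed; the SAP sets them aside for efficacy.

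Two things are at stake.

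- **Possible bias.** A treatment contrast is biased only if non-dosing differs by arm and is also related to prognosis. For high dose against placebo that is unlikely, because the infusion rates are equal and treatment is "blinded by the use of visually identical appearing RNS60 and placebo infusion bags". It is less unlikely for comparisons that involve the low dose, because SAP 2.2.2 accepts that staff giving the infusion may recognise its lower rate.
- **Misreading.** Even without bias, a reader of a result labelled ITT will take it for an all-randomised result. These estimates are meant to inform the powering of a later efficacy trial (Protocol Synopsis and 9.3.3).

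There is also a reporting gap. The listing of eligibility, consent and randomisation in SAP 3.3.6 is limited to ITT, so it omits undosed patients.

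**Working it through.** **Step 1: who is in each set.**

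| Set | Dosing required? | Efficacy analysis assigned? |
|---|---|---|
| Protocol 9.2 ITT | No | Yes, primary |
| SAP 3.2.1 Enrolled | No | No |
| SAP 3.2.3 ITT | Yes | Yes, primary |
| SAP 3.2.4 Per-Protocol | Yes | Yes, secondary |
| SAP 3.2.5 Safety | Yes | No (safety only) |

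SAP 3.2.3 ITT and SAP 3.2.5 Safety have essentially the same members and differ in grouping by randomised or by actual treatment. SAP 3.4.4.1 (Wilcoxon analysis of mRS) and 3.4.4.2 (correlations) name no population. They fall under the set that 3.2.3 makes primary for efficacy data, and nothing in them brings undosed patients in.

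**Step 2: inputs for an illustration.** Neither document gives a figure to reproduce: there is no power calculation, and the number undosed is not stated. The target of 100 at 1:1:1 (SAP 2.2.4, 2.2.2) gives about 33 per arm. Protocol 2.1 says that about half of patients reach functional independence after EVT. I therefore assume 16/33 = 48.5% disabled (mRS 3-6) in each arm, a true odds ratio (OR) of 1.00, and crude two-arm odds ratios.

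SE(log OR) = sqrt[2 × (1/16 + 1/17)] = 0.493.

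**Step 3: effect of removing k undosed patients per arm.**

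(a) *Prognosis-related non-dosing, equal in both arms.* With k = 1, 2 or 3 removed from each arm and the same outcome in all of them, both arms become (16−k)/(33−k) if the undosed are disabled, or 16/(33−k) if they are not. The OR stays 1.00.

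(b) *Prognosis-related non-dosing, arm random.* K undosed patients are drawn from the 32 disabled among 66, and the arm split is hypergeometric (32, 16, K). The mean shift in log OR is 0.

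| K | SD of shift in log OR | SD / SE |
|---|---|---|
| 2 | 0.093 | 0.19 |
| 3 | 0.116 | 0.24 |
| 4 | 0.136 | 0.28 |
| 6 | 0.174 | 0.35 |

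(c) *Worst case: one arm only, all with the same outcome.*

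| k | Undosed all disabled | OR | Undosed all not disabled | OR |
|---|---|---|---|---|
| 1 | 15/32 = 46.9% | 0.94 | 16/32 = 50.0% | 1.06 |
| 2 | 14/31 = 45.2% | 0.88 | 16/31 = 51.6% | 1.13 |
| 3 | 13/30 = 43.3% | 0.81 | 16/30 = 53.3% | 1.21 |

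At k = 3, |ln OR|/SE is 0.42 or 0.39.

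**Step 4: cost of the all-randomised set.** If k of 33 active-arm patients are undosed and respond like placebo, an effect is diluted by k/33 = 3.0%, 6.1% or 9.1%. An assumed 15-point difference becomes 15 × (1 − k/33) = 14.5, 14.1 or 13.6 points.

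**The case against.** The change is not hidden. SAP 3.2.3 states the exclusion, 6.4 repeats it beside the protocol's definition, and the disposition table in 3.3.1 allows undosed counts by arm to be derived. Deviations and medical history are summarised on the Enrolled Population, baseline tables cover every population, and SAP 6.5 says all available data will be listed. The leading contrast is high dose against placebo, where arm-related non-dosing is unlikely. Dosing is due within 30 minutes of randomisation and before arterial access closure, so missed doses may well be logistic. Nothing in the documents says that recognising the low-dose rate affects whether an infusion is started, and low-dose tests rank last. The planned models are longitudinal or covariate-adjusted, so crude odds ratios are only indicative. Efficacy is secondary and unpowered.

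Most of this stands, and it limits the size of the problem. It does not remove the conflict. Disclosure as a clarification, with no reason, does not justify reversing who is included. The general listing statement in 6.5 does not override the specific ITT limit in 3.3.6. It is also fair that a missing baseline infarct volume could affect dosed patients too. That rule is secondary, and the main change does not depend on it.

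**Conclusion.** The concern holds. The two documents define ITT differently, the SAP governs, and under it no efficacy analysis is assigned to all randomised patients. Treatment policy within a dosed set is not a contradiction in itself, but the estimand's population departs from the protocol in the same way.

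The expected numerical effect is small: none if nobody is undosed or if non-dosing is balanced, and about 0.4 SE with three undosed in a single arm. These figures rest on assumed arms of 33, 48.5% disabled, and one to three undosed per arm (two to six in total in the random-split case). Nothing suggests that the change was driven by data, and the primary safety analysis is untouched. It should be corrected because the departure is avoidable and the label misdescribes the set.

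**What to change.** 1. **SAP 3.2.3:** define ITT as all randomised, analysed as randomised (the members of 3.2.1), and use it for the primary efficacy analyses.
2. Keep the randomised-and-dosed set as a separately named modified-ITT sensitivity set.
3. **SAP 3.1.1 and 3.1.3:** both are anchored to infusion start, so anchor analysis day and baseline to randomisation for undosed patients. State one rule for a missing baseline infarct volume, for example imputing the covariate and repeating each model without it. That volume comes from the first post-EVT MRI and is a covariate for mRS, infarct volume, worsening of stroke and Barthel Index; without a rule, undosed patients lacking the scan could drop out again. In the readable text only the infarct sensitivity analysis carries it into imputation.
4. **SAP 2.1.3:** align the estimand population, and list study drug never started as an intercurrent event under treatment policy.
5. **SAP 6.4:** if any departure is kept, report it as a change and give the reason.
6. **SAP 3.3.1 and 3.3.6:** add reasons for non-dosing by arm, and run the eligibility listing on the Enrolled Population.

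**Cost:** SAP wording, reuse of the all-randomised flag, an anchor date for undosed patients, and the missing-covariate rule with its programming in four models, which is the main work. Scheduled visits already follow the CRF label. The statistical price is the 3-9% dilution shown above, if one to three of 33 active-arm patients are undosed.

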3.2.4 Per-Protocol (PP) Population

The PP Population is defined as all subjects who are randomized and receive study drug with no major protocol deviations (PD) that may impact the efficacy assessments. A major PD that would preclude a subject from being included in the PP Population could involve, but is not limited to the following:

- Inclusion/exclusion criteria not met
- Receiving treatment without consent
- Receiving incorrect dose volume (outside of the 48-hour infusion (+/-4 hours)
- Receiving the wrong study drug/placebo IV bag

The PP Population is a secondary population for analysis of the efficacy data. The primary analysis will be repeated on the PP Population. The final criteria for reasons to exclude subjects from the PP Population, along with a list of subjects with major PDs leading to exclusion from the PP Population will be finalized prior to unblinding the randomized treatment assignments.

3.2.5 *Safety Population*

The Safety Population is defined as all randomized subjects who receive any volume of study drug. All safety data will be analyzed using the Safety Population. In the event that a subject is given the incorrect study drug (i.e., received the incorrect assigned randomized study drug), the actual treatment received will be used for analysis.

3.3 Subject Data and Study Conduct

3.3.1 *Subject Disposition*

Subject disposition will be listed by arm.

The number and percentage of subjects in each of the following categories will be presented by treatment and in total for all enrolled subjects:

- Enrolled Population,
- Randomly assigned to study intervention Population,
- ITT Population,
- PP Population,
- Safety Population,
- Completed the study,
- Early terminated the study and if the primary reason is due to COVID-19.

Primary reasons for discontinued study and primary reasons for discontinued study due to COVID-19 will be tabulated.

3.3.2 *Protocol Deviations*

A CSR reportable PD is related to inclusion/exclusion criteria, conduct of the trial, subject management or subject assessment that impact the safety of the subjects or jeopardize the quality of study data. Counts and percentages of subjects with PDs by deviation category, as defined in the protocol deviation plan, will be summarized by treatment and in total based on the Enrolled Population.

Primary reasons for excluding a subject from the PP Population will be summarized.

The following categories will be used for CSR reportable PDs:

- A subject did not meet entry criteria

- A subject received treatment without consent
- A subject was not approached for consent despite regaining capacity
- A subject received the wrong study drug/placebo IV bag
- A subject received an incorrect dose and/or infusion rate
- A subject started study drug/placebo dosing after the mechanical endovascular thrombectomy was completed (arterial access closure)
- Safety labs or assessments were not completed as defined by protocol
- An SAE which was not reported within 24 hours after event was known

Protocol deviations determined to have been related to COVID-19 will be listed. A listing of COVID-19 related non-reportable PDs will be included in an appendix of the CSR.

3.3.3 Demographic and Baseline Characteristics

The following demographic and baseline characteristics will be summarized:

- Age (years) and age categories (<80 years, ≥80 years)
- Sex
- Childbearing potential
- Race
- Ethnicity
- Weight (kg)
- NIHSS and NIHSS categories at baseline (6-10, >10)
- ASPECTS and ASPECTS categories (5-7, 8-10)

Demographic and baseline characteristics will be summarized with descriptive statistics or counts and percentages of subjects as appropriate by treatment and in total for each defined analysis population.

